### 6.4.1 Holding Day 15 NSCs

If Day 15 NSCs and subsequent 5-FC (with leucovorin) are held, resultant start dates are as follows:

- If participant is able to resume treatment by or on Day 22, he/she will resume study agents as soon as logistically feasible during the same treatment cycle. The cycle length would be extended accordingly, so that 14 days between NSC administrations would be maintained.
- If participant is not able to resume treatment by or on Day 22, he/she will continue the current cycle without a second NSC administration and resume study agents at the start of the next treatment cycle. The current cycle would be 28 days in length and the participant will forgo the Day 15 NSCs/ Day 18-24 5-FC (w/ w/o leucovorin).

### 6.4.2 Holding Any of the 5-FC (with Leucovorin) Administrations After NSC Administration

If the 5-FC (with leucovorin) administration is held after the participant has received the corresponding NSC administration, held doses of 5-FC and leucovorin will may be made up by extending the 5-FC administration for up to one day so that there is a minimum of three days without an agent being administered between 5-FC administration and NSC administration. (Example: Pt receives C2D1 NSCs

and has agents held from C2D3-C2D6; participant will resume 5-FC (with leucovorin) the evening of C2D6 through and including C2D11, and then proceed to Day 15 NSC administration per usual.)

## 7.0 Data and Safety Monitoring, Unanticipated Problems and Adverse Event Reporting

---

### 7.1 Data and Safety Monitoring

This is a Risk Level 4 study, as defined in the “City of Hope Data and Safety Monitoring Plan”, <http://www.coh.org/dsmc/Pages/forms-and-procedures.aspx> involving COH as IND holder and gene therapy.

### 7.2 Monitoring and Personnel Responsible for Monitoring

The City of Hope Protocol Management Team (PMT) consisting of the PI, collaborating investigators, CRA, protocol nurse, and statistician is responsible for monitoring the data and safety of this study, including implementation of the stopping rules for safety.

This study will utilize the Phase I tracking log to monitor data and safety for dose escalation, recording doses administered and resultant adverse events. The tracking log will contain dose levels administered, DLT-defining adverse events, and documentation that the data from a dose level is complete before dose escalation. Those data and safety elements will be reported to the COH DSMC as applicable with the PMT report, which will be submitted quarterly from the anniversary date of activation, as noted in Table 1 below. Protocol specific data collection will include the following items: adverse events per dose level, patient outcomes, and protocol deviations.

A decision to escalate to the next dose level will be made by the PMT only after all patients on the current dose level have been observed through day 28. Enrollment of the first 3 patients to dose levels 1-3 will be staggered by requiring that each of these patients be observed for 28 days before the next patient can begin treatment on a particular dose level.

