#### **5.3 Repeat Cycles of Study Treatment**

A treatment cycle is defined as 28 days.

Repeat cycles of study treatment will be administered as long as there is no evidence of progressive disease, and treatment with the NSCs and 5-FC (and leucovorin, as indicated) is well tolerated.

Please see section 6.3 for criteria that the patient must meet in order to or proceed with study treatment on days 1 and 15 of a cycle, as well as instructions for dose modifications if needed with repeat doses of study treatment.

There will be no intra-patient dose escalation of NSCs, 5-FC, or leucovorin.

The NSCs will be administered in the outpatient setting via a Rickham on days 1 and 15 of a cycle, as per section 5.2.4.

5-FC (and leucovorin, as indicated) will be taken by the patient on days 4-10 and days 18-24 as per the dose level the patient is in (see the dose escalation schema table in section 5.1).

Prochlorperazine 10 mg p.o every 6 hours (or a similar strength anti-emetic) will be used as needed.

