**A DLT is defined as an adverse event that:**

- (a) is related to the administration of NSCs, 5-FC, or leucovorin, or any combination of the agents, with an attribution of possible, probable, or definite, and
- (b) occurs during the first treatment cycle (including Cycle 2 Day 1 safety assessments), and
- (c) meets any of the following criteria:

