## 5.6 Study Design

The study will implement a standard 3+3 design. The goal will be to determine the maximum tolerated dose (MTD), which is defined as the highest dose level tested in which fewer than 33% of patients experienced a DLT attributable to the treatment regimen of NSCs with 5-FC and leucovorin, when at least 6 patients were treated at that dose and are evaluable for toxicity. If the MTD has not been reached with 1.5 x 108 NSCs, 37.5 mg/kg q6h 5-FC and 25 mg q6h leucovorin (dose level 3 plus leucovorin), then that dose will be termed the maximum feasible dose (MFD).

- 5.6.1** Phase I cohorts will be of 3 or 6 participants, as indicated by the dose-escalation criteria.
- 5.6.2** The dose schedule is provided in the table in section 5.7. The first cohort of patients will start at dose level 1.
- 5.6.3** Dose escalation will proceed through the identified doses without skipping any dose levels.
- 5.6.4** *Enrollment of the first 3 patients to dose levels 1-3 will be staggered* by requiring that each of the first 3 patients be separately observed for 4 weeks (or until the DLT assessment period has ended) before the next patient can start treatment on that dose level.
- 5.6.5**
- 5.6.6** Dose escalation rules:
  - 5.6.6.1 If 0/3 study participants experiences a DLT, the next cohort of 3 study patients will be treated at the next higher dose level.
  - 5.6.6.2 If 1/3 study participants experiences a DLT, the cohort will be expanded by another 3 study participants who will be treated at the same dose level for a total of 6 study participants.
  - 5.6.6.3 If 1/6 participants experiences a DLT, the next cohort of 3 study participants will be treated at the next higher dose level.
  - 5.6.6.4 If 2 or more participants of either a 3 participant or 6 participant cohort encounter a DLT, then the MTD has been exceeded. If applicable, three (more) participants will be enrolled at the next lower dose level.
  - 5.6.6.5 At least 6 patients will be treated at the MTD (or MFD, if the MTD is not reached).

For a patient to be counted for dose escalation, s/he must receive at least 80% (+/- 5%) of the assigned NSCs on days 1 and 15 and 80% (+/- 5%) of the 5-FC (and leucovorin, as indicated) on days 4-10 and 18-24 during cycle 1 and be followed up to and including cycle 2 day 1 safety assessments or have experienced a DLT.

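### The 28-day stagger gate in section 7.2 can be met before the prior patient's DLT period, which runs through cycle 2 day 1, has ended

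*Combined protocol and SAP*

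**What the plan says.** Two sections set the stagger for the first three patients at each of dose levels 1-3.

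- Section 7.2 staggers them by "requiring that each of these patients be observed for 28 days before the next patient can begin treatment" at that level. It does not mention the DLT window.
- Section 5.6.4 wants each of them "separately observed for 4 weeks (or until the DLT assessment period has ended) before the next patient can start treatment on that dose level". It does not say whether the earlier or the later of the two points applies.

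The DLT period is defined elsewhere. Under section 5.5 an event is a DLT if it is related to treatment, "occurs during the first treatment cycle (including Cycle 2 Day 1 safety assessments), and" meets one of the listed toxicity criteria. The evaluability rule in section 5.6 uses the same end point: a patient who counts for escalation must "be followed up to and including cycle 2 day 1 safety assessments or have experienced a DLT". For escalation, section 7.2 has the Protocol Management Team decide "only after all patients on the current dose level have been observed through day 28".

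Two further sections set the calendar. Section 5.3 states: "A treatment cycle is defined as 28 days". Section 6.4.1 covers a held day 15 cell dose: "If participant is able to resume treatment by or on Day 22, he/she will resume study agents as soon as logistically feasible". The cycle is then lengthened to keep 14 days between cell doses. The general text of section 6.4 says that the day count runs on during a hold and that evaluations keep their original place in the cycle.

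**The concern.** A stagger is there so that one patient's DLT period has been seen before the next patient is exposed at the same level. Section 7.2 gives the monitoring team a fixed count of days, while the DLT period ends at a visit whose date can move. When cycle 1 is extended the two separate, and a team that follows 7.2 to the letter can start the next patient while the prior patient's DLT period, and possibly the second 5-FC course, is still running.

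The study calendar (section 10.0, with its note limiting the days 18-24 visit to day 22) adds to this. After day 22 the next scheduled toxicity assessment, and the next scheduled blood count and chemistry, is at cycle 2 day 1. No cycle 1 day 28 assessment is scheduled. Section 5.5 makes several blood-count events DLTs, so the last part of the window depends on that visit and on adverse events reported between visits.

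**Working it through.** This is calendar arithmetic; no sample-size formula applies.

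**Inputs.** Gate: 28 days (7.2). Cycle length: 28 days (5.3). End of DLT period: cycle 2 day 1 safety assessments (5.5, 5.6). Second cell dose: day 15 on schedule. After a hold, the patient must be able to resume by day 22, with 14 days kept between cell doses (6.4.1). 5-FC: 7 days, starting at least 3 days after the cells (10.0).

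**The plan's own figure.** One cycle is 28 days, so cycle 2 day 1 is 28 + 1 = day 29. The second cell dose gives the same answer: 15 + 14 = 29. On schedule, then, the 28-day gate and the end of the DLT period nearly coincide.

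**With the second cell dose on day r:**
- second 5-FC course: days r + 3 to r + 9
- 5-FC days left after day 28: r + 9 - 28 = r - 19, or 0 if negative
- cycle 2 day 1: day r + 14
- gap: r - 14 days if the next patient starts on day 28, or r - 15 if on day 29 (after 28 full days)

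| r | 5-FC days | 5-FC days left after day 28 | Cycle 2 day 1 | Gap (start day 28 / day 29) |
|---|---|---|---|---|
| 15 | 18-24 | 0 | 29 | 1 / 0 |
| 19 | 22-28 | 0 | 33 | 5 / 4 |
| 20 | 23-29 | 1 | 34 | 6 / 5 |
| 21 | 24-30 | 2 | 35 | 7 / 6 |
| 22 | 25-31 | 3 | 36 | 8 / 7 |

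**Assessments in the r = 22 row.** If evaluations keep their original times (6.4), the day 22 visit falls before 5-FC restarts on day 25. By day 28, 4 of the 7 days of the second course have been taken, with nominally no scheduled toxicity or blood assessment during it. The ±3 day test window can shift the visit. On schedule, the same window puts the cycle 2 day 1 assessments anywhere from 29 - 3 = day 26 to 29 + 3 = day 32.

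**If the patient cannot resume by day 22,** 6.4.1 keeps the cycle at 28 days and the planned cycle 2 day 1 stays at day 29.

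**Releases within the first three patients.** Patient 1 to 2 and patient 2 to 3, at three levels: 2 × 3 = 6. A single DLT does not close a level: "If 1/3 study participants experiences a DLT, the cohort will be expanded by another 3 study participants". Two DLTs do (5.6.6.4). A late DLT can therefore change a release by rule only from patient 2 to patient 3, and only if patient 1 already had a DLT. That is 3 of the 6. For the other 3 the stagger protects by observation alone.

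**The case against.** The best reply is that 7.2 sets a minimum and does not order a start on day 28. A team can satisfy 7.2, 5.6.4 and 5.5 together by waiting for the latest point. Section 5.6.4 already mentions the end of the DLT period, and section 13.2 describes entry as following the prior patient's completion of cycle 1, which suggests the intent. On schedule the difference is a day at most, and anything larger needs a held day 15 dose that is later given in the same cycle.

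Much of this stands. It shows that the conflict is narrow and that the intent was probably sound. It does not remove the conflict: a minimum that can be met too early is still the stated gate, the alternative in 5.6.4 has no rule for choosing, and 13.2 is an accrual forecast.

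The reply is also right about the dates. A reader might infer from 6.4.1 that day 36 is the latest possible cycle 2 day 1, or that dosing can run past day 28 only if the cells are given on days 20-22. The documents do not support either bound. Day 22 limits when the patient must be able to resume, and the dose then follows when logistics allow. The calendar gives cell doses ±1 day (a dose on day 23 would put cycle 2 day 1 on day 37), and the start-of-cycle criteria in 6.3.2 can delay cycle 2 further.

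**Conclusion.** The point holds as a reconciliation of a safety gate, of minor to should-fix weight. Section 7.2 read literally, and one reading of 5.6.4, allow the next staggered patient to start before the prior patient's DLT period under 5.5 and 5.6 has ended. The gap is 0-1 day on schedule and 7-8 days in the day 22 example. That example assumes nominal days, the minimum 3-day wait before 5-FC, and that the cycle 2 day 1 assessments move with the extended cycle, which 6.4 leaves unclear.

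A reader might go further and infer that escalation rests on incomplete DLT data, or that the MTD is biased. The documents do not support this. The 5.6 evaluability rule requires follow-up through the cycle 2 day 1 assessments, or a DLT, before a patient counts, so escalation and expansion decisions are already protected. The day 28 wording on escalation in 7.2 is an inconsistency of text only. No probability is attached to the sequence in which the stagger would change a decision, because the documents give no rate of day 15 holds.

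**What to change.** - Reword 7.2 and 5.6.4 to agree with 5.5 and 5.6: the next staggered patient starts no earlier than 28 days and not before the end of the prior patient's protocol-defined DLT assessment period, including cycles extended under 6.4.1. Keeping 28 days as the minimum stops an assessment done early in its window, such as on day 26, from bringing the start forward.
- Align the escalation wording in 7.2 in the same way.
- State how the original-times rule in 6.4 fits with the extended cycle in 6.4.1 for the cycle 2 day 1 assessments.
- Have the sponsor state when the DLT period ends for a patient whose cycle 2 is delayed, or who never starts it, for example one removed under 5.8.1. The documents do not say, and this review does not supply a rule.

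**Cost.** This is a wording change. It adds 0-1 day per on-schedule release, so 6 × 0 to 6 × 1 = 0-6 days over the six releases, against a planned accrual of 30-36 months. In the day 22 example it adds about 7-8 days for that patient, possibly a few more with visit windows or a delayed cycle 2. The section 13.1 figures depend on six patients at the MTD and not on the stagger, so they do not change.

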**Table 1: City of Hope PMT Reporting Timelines for the DSMC**

Risk Level	Phase	Standard Reporting Requirement
RL 1, RL2, and Compassionate Use Studies	No reports required	
3	I	Every 3 months from activation date, as indicated in MIDAS
3	Pilot, Feasibility, II-IV	Every 6 months from activation date, as indicated in MIDAS
4	Pilot, Feasibility, I-IV	Every 3 months from activation date, as indicated in MIDAS

Data and safety will also be reported to the FDA. All IND safety reports that are submitted to the FDA regarding this protocol will also be submitted to the COH DSMC for review. As required by the FDA, study patients will be followed long term (up to 15 years or until they die; see section 5.11), and the PMT will continue to report data and safety concern to the FDA and DSMC as they arise during this follow-up period.

### 7.3 Definitions

**Adverse event (AE)** - An adverse event is any untoward medical experience or change of an existing condition that occurs during or after treatment, whether or not it is considered to be related to the protocol intervention.

**Unexpected Adverse Event [21 CFR 312.32 (a)]** – An adverse event is unexpected if it is not listed in the investigator's brochure and/or package insert; is not listed at the specificity or severity that has been observed; is not consistent with the risk information described in the protocol and/or consent; is not an expected natural progression of any underlying disease, disorder, condition, or predisposed risk factor of the research participant experiencing the adverse event.

**Expected Adverse Event** - Any event that does not meet the criteria for an unexpected event OR is an expected natural progression of any underlying disease, disorder, condition, or predisposed risk factor of the research participant experiencing the adverse event

**Serious Adverse Event (SAE) [21 CFR 312.32]** is defined as any expected or unexpected adverse event that results in any of the following outcomes:

- Death
- Is life-threatening event (places the subject at immediate risk of death from the event as it occurred);
- Requires in-patient hospitalization (not required as part of the treatment) or prolongation of existing hospitalization;
- A persistent or significant disability/incapacity;
- A congenital anomaly/birth defect
- Secondary Malignancy, or
- Any other adverse event that, based upon appropriate medical judgment, may jeopardize the subject's health and may require medical or surgical intervention to prevent one of the outcomes listed above (examples of such events include allergic bronchospasm requiring intensive treatment in the emergency room or at home, blood dyscrasias of convulsions that do not result in inpatient hospitalization, or the development of drug dependency or drug abuse).

**Unanticipated problem (UP)** – Any incident, experience or outcome that meets all three of the following criteria:

1. Unexpected (in term nature, severity, or frequency) given the following: a) the research procedures described in the protocol-related documents such as the IRB approved research protocol, informed consent document or Investigator Brochure (IB); and b) the characteristics of the subject population being studied; **AND**
2. Related or possibly related to participation in the research (possibly related means there is a reasonable possibility that the incident, experience, or outcomes may have been caused by the drugs, devices or procedures involved in the research); **AND**
3. Suggests that the research places subjects or others at greater risk of harm (including physical, psychological, economic, or social harm) than previously known or recognized.

### 7.4 Reporting of Unanticipated Problems and Adverse Events

**Unanticipated Problems:** Unanticipated problems must be reported to the COH DSMC and IRB **within 5 calendar days** according to definitions and guidelines at <http://www.coh.org/hrpp/Pages/hrpp-policies.aspx>. Any unanticipated problem that occurs during the study conduct will be reported to the DSMC and IRB by submitting electronically in iRIS (<http://iris.coh.org>).

**Serious Adverse Events** - All SAEs occurring during this study, whether observed by the physician, nurse, or reported by the patient, will be reported according to definitions and guidelines at <http://www.coh.org/hrpp/Pages/hrpp-policies.aspx> and Table 1 below. Those

SAEs that require expedited reporting will be submitted electronically in iRIS (<http://iris.coh.org/>).

**Adverse Events** - Adverse events will be monitored by the PMT. Adverse events that do not meet the criteria of serious adverse event or are not unanticipated problems will be reported only at the time of protocol continuation reports (see Table 1 below).

**Table 2: City of Hope Adverse Event and Unanticipated Problem Reporting Timelines for the DSMC and IRB**

**Required Reporting Timelines to DSMC for AE/SAEs**  
**Investigator Initiated Studies**

Required Reporting Timeframe to DSMC		
Attribution	UNEXPECTED	EXPECTED
	Death while on active treatment or within 30 days of last day of treatment	
Possibly, Probably, Definitely	5 calendar days	
Unlikely, Unrelated		
	Death after 30 days of last active treatment/therapy	
Possibly, Probably, Definitely	5 calendar days	No reporting required
Unlikely, Unrelated	No reporting required	No reporting required
	Grades 3 and 4 AND meeting the definition of "serious"	
Possibly, Probably, Definitely	5 calendar days	10 calendar days
Unlikely, Unrelated	5 calendar days	10 calendar days
	Grades 1 and 2 AND resulting in "hospitalization"	
Possibly, Probably, Definitely	5 calendar days	10 calendar days
Unlikely, Unrelated	10 calendar days	10 calendar days

An event determined by the IRB of record to be an Unanticipated Problem (UP) will be communicated to the Investigator and COH DSMC through the COH IRB Operations Director. The DSMC will review the case and make a determination as to whether the study will be suspended, terminated, amended, or allowed to continue without amendment.

Required Reporting Timeframe to IRB of Record		
Attribution	UNEXPECTED	EXPECTED
Death		
Possibly, Probably, Definitely	5 calendar days	Annual
Unlikely, Unrelated	Annual	Annual
Grades 3 and 4 AND meeting the definition of a UP		
Possibly, Probably, Definitely	5 calendar days	Annual
Unlikely, Unrelated	Annual	Annual
Grade 1 and 2 AND meeting the definition of a UP		
Possibly, Probably, Definitely	5 calendar days	Annual
Unlikely, Unrelated	Annual	Annual

## 7.5 ADDITIONAL REPORTING REQUIREMENTS

SAEs meeting the requirements for expedited reporting to the FDA, as defined in 21 CFR 312.32, will be reported as an IND safety report using the MedWatch Form FDA 3500A for Mandatory Reporting which can be found at:

<http://www.fda.gov/Safety/MedWatch/HowToReport/DownloadForms/default.htm>

The PI or designee will be responsible for contacting the Office of IND Development and Regulatory Affairs (OIDRA) at COH to ensure prompt reporting of safety reports to the FDA. OIDRA will assist the PI with the preparation of the report and submit the report to the FDA in accordance with the following:

- any unexpected fatal or life threatening adverse experience associated with use of the drug must be reported to the FDA no later than 7 calendar days after initial receipt of the information [21 CFR 312.32(c)(2)];
- any adverse experience associated with use of the drug that is both serious and unexpected must be submitted no later than 15 calendar days after initial receipt of the information [21 CFR 312.32(c)(1)]

- any follow-up information to a study report shall be reported as soon as the relevant information becomes available. [21 CFR 312.32(d)(3)]

### **Medical Device Reportable Events**

Medical devices that will be used in this study include intracerebral microdialysis catheters and Rickham reservoir/catheter systems.

Medical Device Reportable (MDR) Events are the AEs or problems that the medical device regulation requires to be reported. These events include patient deaths and serious injuries that the medical devices have or may have caused or contributed to, i.e., the devices may have directly caused the events or played a role in the events.

The timely reporting of MDR reportable events is required by the FDA, and will be handled by OIDRA.

### **National Institutes of Health-Office of Biotechnology Activities (NIH-OBA) and FDA Reporting**

Since this study involves gene therapy, and City of Hope holds the IND, adverse events must also be reported to the NIH-OBA.

The PI/designee will submit the adverse event report through the City of Hope electronic reporting system, and then OIDRA will take responsibility for reporting of the adverse event to NIH-OBA.

